### 13.14 Dose Modification

#### 13.14.1 Phase 1

PLX3397 or temozolomide dose reductions and interruptions will be permitted during the 11-week DLT window (Cycle 1 through Cycle 2, i.e., 1 week PLX3397 run-in, 6 weeks of PLX3397 + RT + temozolomide, and 4 weeks of post-RT recovery) only if a patient experiences a DLT (see [Section 13.13.2](#) Dose-Limiting Toxicities). PLX3397 interruptions during the 11-week DLT window are also permitted for Grade 3 vomiting that persists despite optimal supportive care.

If a patient experiences a DLT during the 11-week DLT window, treatment continuation at a lower dose may be permitted at the discretion of the Investigator and in consultation with the Medical Monitor. PLX3397 dose reductions should occur in increments of 200 mg/day, depending on the toxicity grade, as noted in [Table 3](#), PLX3397 Dose Modifications. For dose reductions see [Section 13.13.1](#) Dose Escalation.

If dose interruption continues after the patient's scheduled C3D1 PLX3397 dose administration, the patient should discontinue study treatment and have the procedures outlined in [Section 13.11](#) End of Treatment.

During the adjuvant treatment period, PLX3397 or temozolomide dose reductions and interruptions will be permitted in consultation with the Medical Monitor. PLX3397 dose reductions should occur in increments of 200 mg/day, depending on the toxicity grade, as noted in [Table 3](#) PLX3397 Dose Modifications. For dose reductions see [Section 13.13.1](#) Dose Escalation.

If a patient experiences a DLT, temozolomide dose reduction should be made according to the prescribing information noted in [Attachment 4](#) and also summarized in [Section 16](#).

### 13.14.2 Phase 2

Phase 2 will not include a separate dose escalation design, as there has been no delayed toxicity observed for PLX3397 in extensive nonclinical and clinical evaluations to date, and temozolomide is given at a lower intensity schedule compared to the daily schedule during concomitant radiation therapy. During Phase 2, reduction/interruption of dosing for adverse events may take place at any time during the study according to the guidelines in Table 3.1, Table 3.2, and Table 3.3.

Dose reduction/interruption guidelines for hematologic and nonhematologic treatment-related TEAEs are based on severity. Dose interruptions can be implemented at the discretion of the treating Investigator to manage intolerable or clinically significant toxicity. If a dose interruption is required, study assessments should be performed as scheduled, irrespective of the study drug delay, with the exception of PK assessments, which should be deferred until treatment is resumed. Interruptions due to toxicity lasting >14 days require treatment discontinuation unless the medical monitor approves continuation.

Dose reductions of temozolomide should be made according to the prescribing information noted in [Attachment 4](#) and also summarized in [Section 16](#).

Below are guidelines for dosage modification for PLX3397-related toxicities as well as guidelines for their management. Dose reductions should occur in increments of 200 mg/day, depending on the toxicity grade, as noted in [Table 3](#), [Table 4](#), and [Table 5](#). As the capsules are provided in 200 mg strengths, dose reduction should occur by a reduction of one capsule from either the morning or evening dose.

Up to 5 days of treatment interruption are permitted for any reason. Interruptions of 6 to 7 treatment days will be considered an acceptable protocol deviation. For interruptions of 8 days or greater, continuation of patients in the study should be discussed with the medical monitor.

Temozolomide dose reduction should be made according to the prescribing information noted in [Attachment 4](#) and also summarized in [Section 16](#).

These parameters are only a guide and are not intended to supersede the clinical judgment of the treating physician. All adjustments should be made in consultation with the Medical Monitor.

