### 2 DOSAGE AND ADMINISTRATION

#### 2.1 Recommended Dosing and Dose Modification Guidelines

The recommended dose for TEMODAR as an intravenous infusion over 90 minutes is the same as the dose for the oral capsule formulation. Bioequivalence has been established only when TEMODAR for Injection was given over 90 minutes [see *Clinical Pharmacology* (12.3)]. Dosage of TEMODAR must be adjusted according to nadir neutrophil and platelet counts in the previous cycle and the neutrophil and platelet counts at the time of initiating the next cycle. For TEMODAR dosage calculations based on body surface area (BSA) see **Table 5**. For suggested capsule combinations on a daily dose see **Table 6**.

**Patients with Newly Diagnosed High Grade Glioma: Concomitant Phase:** TEMODAR is administered at 75 mg/m^2 daily for 42 days concomitant with focal radiotherapy (60 Gy administered in 30 fractions) followed by maintenance TEMODAR for 6 cycles. Focal RT includes the tumor bed or resection site with a 2- to 3-cm margin. No dose reductions are recommended during the concomitant phase; however, dose interruptions or discontinuation may occur based on toxicity. The TEMODAR dose should be continued throughout the 42-day concomitant period up to 49 days if all of the following conditions are met: absolute neutrophil count greater than or equal to 1.5 x 10^9/L, platelet count greater than or equal to 100 x 10^9/L, common toxicity criteria (CTC) nonhematological toxicity less than or equal to Grade 1 (except for alopecia, nausea, and vomiting). During treatment a complete blood count should be obtained weekly. Temozolomide dosing should be interrupted or discontinued during concomitant phase according to the hematological and nonhematological toxicity criteria as noted in **Table 1**. *Pneumocystis carinii* pneumonia (PCP) prophylaxis is required during the concomitant administration of TEMODAR and radiotherapy, and should be continued in patients who develop lymphocytopenia until recovery from lymphocytopenia (CTC Grade less than or equal to 1).

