**TABLE 1: Temozolomide Dosing Interruption or Discontinuation During Concomitant Radiotherapy and Temozolomide**

Toxicity	TMZ Interruption*	TMZ Discontinuation
Absolute Neutrophil Count	greater than or equal to 0.5 and less than 1.5 x 10  /L	less than 0.5 x 10  /L
Platelet Count	greater than or equal to 10 and less than 100 x 10  /L	less than 10 x 10  /L
CTC Nonhematological Toxicity (except for alopecia, nausea, vomiting)	CTC Grade 2	CTC Grade 3 or 4

\*Treatment with concomitant TMZ could be continued when all of the following conditions were met: absolute neutrophil count greater than or equal to 1.5 x 10^9/L; platelet count greater than or equal to 100 x 10^9/L; CTC nonhematological toxicity less than or equal to Grade 1 (except for alopecia, nausea, vomiting). TMZ=temozolomide; CTC=Common Toxicity Criteria.

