**Note:** Grade 5 (fatal) adverse reactions are included in the Grade ≥3 column.

Myelosuppression (neutropenia and thrombocytopenia), which is a known dose-limiting toxicity for most cytotoxic agents, including TEMODAR, was observed. When laboratory abnormalities and adverse reactions were combined, Grade 3 or Grade 4 neutrophil abnormalities including neutropenic

reactions were observed in 8% of the patients, and Grade 3 or Grade 4 platelet abnormalities, including thrombocytopenic reactions, were observed in 14% of the patients treated with TEMODAR.

**Refractory Anaplastic Astrocytoma:** Tables 8 and 9 show the incidence of adverse reactions in the 158 patients in the anaplastic astrocytoma study for whom data are available. In the absence of a control group, it is not clear in many cases whether these reactions should be attributed to temozolomide or the patients' underlying conditions, but nausea, vomiting, fatigue, and hematologic effects appear to be clearly drug-related. The most frequently occurring adverse reactions were nausea, vomiting, headache, and fatigue. The adverse reactions were usually NCI Common Toxicity Criteria (CTC) Grade 1 or 2 (mild to moderate in severity) and were self-limiting, with nausea and vomiting readily controlled with antiemetics. The incidence of severe nausea and vomiting (CTC Grade 3 or 4) was 10% and 6%, respectively. Myelosuppression (thrombocytopenia and neutropenia) was the dose-limiting adverse reaction. It usually occurred within the first few cycles of therapy and was not cumulative.

Myelosuppression occurred late in the treatment cycle and returned to normal, on average, within 14 days of nadir counts. The median nadirs occurred at 26 days for platelets (range: 21-40 days) and 28 days for neutrophils (range: 1-44 days). Only 14% (22/158) of patients had a neutrophil nadir and 20% (32/158) of patients had a platelet nadir, which may have delayed the start of the next cycle. Less than 10% of patients required hospitalization, blood transfusion, or discontinuation of therapy due to myelosuppression.

In clinical trial experience with 110 to 111 women and 169 to 174 men (depending on measurements), there were higher rates of Grade 4 neutropenia (ANC less than 500 cells/ $\mu$ L) and thrombocytopenia (less than 20,000 cells/ $\mu$ L) in women than men in the first cycle of therapy (12% vs. 5% and 9% vs. 3%, respectively).

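### In the Phase 1b DLT window, Section 13.14.1 permits no label-based temozolomide interruption before a DLT, and it conflicts with Section 13.13.3 on liver abnormalities

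*Combined protocol and SAP*

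**What the plan says.** **Rule for the window.** Section 13.14.1 states that "PLX3397 or temozolomide dose reductions and interruptions will be permitted during the 11-week DLT window" and limits this with "only if a patient experiences a DLT". The one exception is a PLX3397 interruption for Grade 3 vomiting that persists under supportive care. It does not extend to temozolomide. The section later adds: "If a patient experiences a DLT, temozolomide dose reduction should be made according to the prescribing information".

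**Temozolomide label (Attachment 4).** Label section 2.1 says: "No dose reductions are recommended during the concomitant phase; however, dose interruptions or discontinuation may occur based on toxicity". Label Table 1 sets the interruption bands at ANC "greater than or equal to 0.5 and less than 1.5 x 10"^9/L and platelets "greater than or equal to 10 and less than 100 x 10"^9/L, and also interrupts for Grade 2 non-hematologic toxicity other than alopecia, nausea and vomiting.

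**DLT list (Section 13.13.2).** The hematologic DLTs are febrile neutropenia of Grade 3 or worse, Grade 4 neutropenia for more than 7 days, and platelets at or below 50 for more than 7 days. Non-hematologic DLTs need Grade 3 or worse and a probable relation to study drug. A Grade 3 AST or ALT rise that settles to Grade 2 or lower within 21 days is excepted.

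**Liver (Section 13.13.3).** This section sits under the Phase 1b heading 13.13. It tells sites to respond to abnormal liver tests by lowering the dose, pausing or stopping, and sets no DLT condition. It generally advises against rechallenge above 5 x ULN.

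**The concern.** A Phase 1b patient on radiotherapy and temozolomide can have a count at which the attached label pauses temozolomide while the protocol does not permit a pause. Weekly hematology in the Phase 1b flow chart would show the low count. What is missing is a permitted action between full dose and permanent discontinuation.

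For the liver, two sections that both apply in Phase 1b give different instructions for a rise that is not a DLT. Sites could therefore handle the same event differently within a cohort of about 7 patients, of whom 6 decide whether the dose is acceptable.

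The exposed period is shorter than 11 weeks. PLX3397 is given for 1 + 6 = 7 weeks and temozolomide for 6. Neither is given in the 4-week recovery (Section 16.1).

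**Working it through.** The plan gives no figure to reproduce here. The check compares each label trigger with the DLT definitions, because Section 13.14.1 makes a DLT the condition for a hold.

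**1. Label triggers against DLTs.** Two readings are needed. The DLT text prints the platelet limit per microliter; it is taken here as x 10^9/L and as covering any count at or below 50. Grade 4 neutropenia is ANC below 0.5 x 10^9/L, from label section 6.1: "higher rates of Grade 4 neutropenia (ANC less than 500 cells" per microliter.

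| Label trigger for interruption | DLT under 13.13.2? | Hold permitted by 13.14.1? |
|---|---|---|
| ANC 0.5 to <1.5, no fever | Never (Grade 4 lies below this band) | No |
| ANC in that band with Grade 3 or worse febrile neutropenia | Yes | Yes |
| Platelets >50 to <100 | Never | No |
| Platelets 10 to 50 | Only after more than 7 days | Not in the first 7 days |
| Grade 2 non-hematologic | Never | No |

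**2. Search for another Phase 1b hold rule for temozolomide.**
- Section 16.1 has the drug given without a break through radiotherapy and contains no toxicity rule.
- Section 16.2 and Table 8 cover the adjuvant period.
- The 5-day allowance, investigator discretion and clinical-judgment text stand in Section 13.14.2, which is Phase 2. The 5-day text recurs only in Section 15.5, on radiation compliance.
- Section 16.3 refers to the full label but does not override Section 13.14.1.
- Section 26.0 allows departures only for apparent immediate hazards.
- Section 13.14.1 restricts reductions and interruptions, not permanent discontinuation, and Section 13.15 leaves stopping study drug open.

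**3. Size of the delay for platelets 10 to 50.** Planned concomitant doses: 6 weeks x 7 days = 42. The label interrupts at the first such count; the DLT needs more than 7 days.
- About 7 extra doses: 7/42 = 16.7%.
- If duration is shown only by weekly counts, a second low count on day 7 does not establish more than 7 days, so the wait can run to day 14: 14/42 = 33.3%.

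Both figures require platelets to stay at or below 50 and enough radiotherapy days to remain. If the count recovers to between 50 and 100, no DLT occurs and the label would still hold. If the first low count falls in the last week of radiotherapy, fewer than 7 doses remain. Section 18.0 also allows more frequent testing, which shortens the second case.

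**4. Frequency, for context only.** For about 35 Phase 1b patients:
- Label Table 7, RT+TMZ, n = 288: any thrombocytopenia 11, so 35 x 11/288 = 1.3; Grade 3 or worse 8, so 35 x 8/288 = 1.0.
- Label section 6.1, laboratory and reaction data combined, phase not stated: "Grade 3 or Grade 4 platelet abnormalities, including thrombocytopenic reactions, were observed in 14% of the patients", so 35 x 0.14 = 4.9. Grade 3-4 neutrophil abnormalities 8%, so 35 x 0.08 = 2.8.

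These rates are without PLX3397 and do not count patients in the label's hold bands, which are not tabulated.

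**5. Liver sections side by side.** Section 13.13.3 offers reduction and interruption for liver abnormalities without a DLT; Section 13.14.1 permits both in the window only after one. Grade 2 AST or ALT (>3 to 5 x ULN) is never a DLT, so the two disagree directly. For Grade 3, DLT status before day 21 is not stated. Section 13.14.1 sends PLX3397 reductions to Table 3, whose title excludes liver function. Table 4, which holds study drug at Grade 2, sits under Phase 2.

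Section 7.5 reports AST or ALT rises in about half of patients at 600 mg/day or more, typically to about 1.5 x ULN, which is below Grade 2. The Grade 2 rate is not given. At an assumed 5%, 10% or 15%, the expected number of 35 is 1.75, 3.5 or 5.25.

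**The case against.** Limiting dose changes during DLT assessment is a legitimate choice: it protects the evaluation of the dose. Sites also have the label, which contains Table 1. They may stop treatment permanently, and Section 26.0 covers immediate hazards. The replacement rule (more than 7 missed PLX3397 days for non-DLT reasons) shows that shorter misses were foreseen. Grade 2 liver rises call for testing two or three times weekly.

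Much of this narrows the point, but it does not supply a temozolomide hold. Attaching a label does not override an explicit condition. The replacement rule settles evaluability for PLX3397 and authorizes no hold. The hazard clause would not ordinarily reach platelets of 80 or ANC of 1.2 x 10^9/L.

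Four stronger readings are tempting and are not supported:
- *PLX3397 liver holds are forbidden without a DLT.* Section 13.13.3 is the more specific text and belongs to Phase 1b, so a site could reasonably follow it. The documents show an unresolved conflict.
- *Every patient with platelets of 10 to 50 receives at least 7 extra doses.* That holds only under the conditions in step 3 of the working.
- *After a DLT during radiotherapy, the protocol orders a dose reduction that the label does not recommend.* The sentence about following the prescribing information comes directly after the adjuvant-period paragraph and cites Section 16, whose reduction rules are adjuvant. The adjuvant period also has its own 8-week DLT observation. It can be read as adjuvant-only.
- *Sites must give full dose whatever the count.* Permanent discontinuation and the hazard clause remain.

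**Conclusion.** The point holds for temozolomide. In the Phase 1b window, most of the label's interruption range cannot meet the Section 13.14.1 condition, and the rest meets it only with febrile neutropenia or after more than 7 days of platelets at or below 50. Apart from permanent discontinuation and immediate hazards, no label-based hold is permitted until a DLT has occurred. The delay of about 7 of 42 doses (17%), or up to 14 (33%) with weekly counts alone, is conditional on sustained low platelets and remaining radiotherapy days. The number of patients affected cannot be derived from the documents.

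For the liver, the supported conclusion is a conflict between Sections 13.13.3 and 13.14.1 for non-DLT rises, clearest at Grade 2, with no statement of which prevails. The 5-15% rate is an assumption.

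This should be fixed, because the written rule is less protective than the label the protocol itself attaches.

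**What to change.** Amend Section 13.14.1 so that, within the 11-week window:

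- (a) temozolomide is interrupted or discontinued according to Attachment 4 Table 1, whether or not a DLT has occurred;
- (b) PLX3397 may be held or reduced for liver abnormalities according to Section 13.13.3, whether or not they are DLTs, keeping that section's limits on rechallenge.

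Leave the DLT definitions, their scoring and the rule on more than 7 missed PLX3397 days as they are.

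The cost is protocol wording and some lost dose intensity in the window for a few patients. A non-DLT PLX3397 hold of more than 7 days would trigger replacement under Section 13.13.1, so an occasional extra patient may be needed. Temozolomide holds do not count toward that rule.

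### In Phase 1b, Section 13.14.1 bars a temporary temozolomide hold during radiotherapy unless a DLT occurs, at counts and toxicity grades where the attached label calls for one

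*Combined protocol and SAP*

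**What the plan says.** Section 13.14.1 (Phase 1) sets the rule for both drugs: "PLX3397 or temozolomide dose reductions and interruptions will be permitted during the 11-week DLT window", a window described as the PLX3397 run-in, "6 weeks of PLX3397 + RT + temozolomide, and 4 weeks of post-RT recovery) only if a patient experiences a DLT". One exception follows: "PLX3397 interruptions during the 11-week DLT window are also permitted for Grade 3 vomiting that persists despite optimal supportive care". It names PLX3397 and not temozolomide. The section's pointer to the label carries the same condition: "If a patient experiences a DLT, temozolomide dose reduction should be made according to the prescribing information noted in" Attachment 4 and Section 16.

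Section 16.1 orders continuous daily temozolomide at 75 mg/m2 through radiotherapy and gives no toxicity-based hold rule. Tables 7 and 8 cover maintenance only.

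The label in Attachment 4, section 2.1, says: "Temozolomide dosing should be interrupted or discontinued during concomitant phase according to the hematological and nonhematological toxicity criteria as noted in" its Table 1. The interruption column there has three triggers:

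- ANC "greater than or equal to 0.5 and less than 1.5 x 10" (to the ninth, per litre)
- platelets "greater than or equal to 10 and less than 100 x 10" (same unit)
- CTC Grade 2 non-hematologic toxicity, with alopecia, nausea and vomiting excepted

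The label recommends no dose reductions in this phase, so a hold is its only step short of stopping the drug.

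**The concern.** The protocol and its own attachment give opposite instructions for the same patient on the same day. Hematology is drawn weekly through radiotherapy (Synopsis, Study Procedures; Phase 1b flow chart), so sites will see these values when they occur.

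A site that obeys Section 13.14.1 and keeps the patient on temozolomide continues a daily cytotoxic drug at counts where the label pauses it. A site that pauses the drug departs from the protocol. Permanent discontinuation remains open, but it takes away a standard-of-care drug that may have needed only a short break. This is the phase that establishes whether PLX3397 can be given with radiotherapy and temozolomide. The nonclinical summary (Section 7.4) reports bone marrow depletion with PLX3397 in rats and dogs, so low counts are a foreseeable event.

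**Working it through.** The plan gives no figure to reproduce. The check sets the label's hold bands against the DLT definitions, looks for any other text that would allow the hold, and then sizes the effect.

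**1. Which label hold bands are DLTs?** The DLT definitions are in Section 13.13.2. Label section 6.1 gives Grade 4 neutropenia as ANC below 500 cells/uL, that is 0.5 x10^9/L. The protocol's platelet limit is printed as 50.0/uL. I read it as 50 x10^9/L and as including lower counts, which favours the protocol.

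| Label hold band during RT | Relevant DLT | Hold allowed under 13.14.1? |
|---|---|---|
| ANC 0.5 to <1.5 | Grade 4 neutropenia (<0.5) for more than 7 days, or febrile neutropenia | No, unless febrile neutropenia |
| Platelets >50 to <100 | None | Never |
| Platelets 10 to 50 | Platelets at or below 50 for more than 7 days | Not in the first 7 days |
| Non-hematologic Grade 2 (with the label's exceptions) | Grade 3 or higher, probably related to study drug | Never, except liver tests (step 2) |

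**2. Does any other text allow the hold in Phase 1b?**

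- Section 13.13.3 allows treatment interruption for liver laboratory abnormalities without requiring a DLT. Liver tests are therefore not clearly barred.
- Section 13.14.2 allows interruption at the investigator's discretion, defers to clinical judgment, and permits up to 5 days off treatment for any reason. All of this stands under the Phase 2 heading.
- Section 15.5 repeats the 5-day allowance within the radiation compliance criteria, where it is best read as radiotherapy interruption.
- Section 13.15 covers permanent discontinuation. Section 26.0 allows changes to remove an immediate hazard. Neither provides an ordinary temporary hold.

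**3. Doses affected per patient.** Temozolomide is taken daily for 6 weeks: 6 x 7 = 42 doses of 75 mg/m2. Radiotherapy day 1 is C1D8 and Cycle 1 lasts 28 days, so the scheduled counts fall on the RT days below. Doses from a count to the end of the course = 43 - RT day.

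| Count first seen | RT day | Doses left | Share of 42 | mg/m2 (doses x 75) |
|---|---|---|---|---|
| C1D15 | 8 | 35 | 83% | 2625 |
| C1D22 | 15 | 28 | 67% | 2100 |
| C2D1 | 22 | 21 | 50% | 1575 |
| C2D8 | 29 | 14 | 33% | 1050 |
| C2D15 | 36 | 7 | 17% | 525 |

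These are ceilings for the bands that never become a DLT. They assume the value stays in the band and nobody stops the drug permanently. For platelets of 10 to 50, about 7 doses pass before the duration condition can be met: 7 x 75 = 525 mg/m2, and 7/42 = 17%.

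**4. How often?** The documents do not tabulate these bands during radiotherapy. The nearest figures are in label section 6.1. In its Table 7, thrombocytopenia as a reported reaction on RT plus temozolomide was 11/288 (4%) at any grade and 8/288 (3%) at Grade 3 or higher. With laboratory values included and phases not separated, Grade 3 or 4 abnormalities occurred in 8% (neutrophils) and 14% (platelets) of temozolomide-treated patients. None of these patients is described as receiving PLX3397. If about 35 Phase 1b patients had the reported-reaction rate, that would be 35 x 11/288 = 1.3 patients. This is a rough scale only, since it counts neither neutrophil holds nor Grade 2 holds.

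**The case against.** The literal conflict is hard to dispute, so the other side goes mainly to weight.

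- **The label is in the protocol without a DLT condition.** Section 16.3 directs the reader to Attachment 4 in both phases, and the Synopsis calls temozolomide standard of care. A site could treat the label as governing. But Section 16.3 says only where the label is, while Section 13.14.1 names temozolomide and uses the word only. No precedence is stated.
- **Restricting dose changes in a DLT window keeps the assessment interpretable.** That is a sound reason for restricting PLX3397, the drug being escalated. It does not justify overriding the safety holds of the background drug, and those holds can be recorded.
- **The top of the dose range is unlikely.** A count would have to stay in the band for five weeks on daily drug with no DLT and no permanent stop. This stands: 35 doses is a ceiling and not an expectation.
- **Few patients may be affected.** Phase 1b is about 35 patients, and the reported thrombocytopenia rate is low. From 01 October 2017 visits and laboratory tests move to about every 12 weeks, which suggests, though the protocol does not say so, that radiotherapy-phase dosing was expected to be over by then. This bears on how many patients an amendment would protect. It does not make the rule correct.

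**Conclusion.** The concern holds, with high confidence, and should be fixed. In Phase 1b, Section 13.14.1 as written does not permit the temporary temozolomide hold that the attached label calls for in these cases:

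- ANC 0.5 to <1.5 x10^9/L without febrile neutropenia
- platelets >50 to <100 x10^9/L
- platelets 10 to 50 x10^9/L for the first 7 days
- non-hematologic Grade 2 toxicity other than alopecia, nausea, vomiting and liver tests

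The cost to a patient in the third case is about 7 doses. In the others it can reach every remaining radiotherapy dose under the persistence assumption stated above. The number of patients affected cannot be derived from the documents. The conclusion rests on reading the platelet DLT limit as 50 x10^9/L including lower counts, and on reading the permissive clauses of Section 13.14.2 as confined to Phase 2. No conflict is claimed for Phase 2, for permanent discontinuation, or for changes made to remove an immediate hazard.

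**What to change.** Amend Section 13.14.1 so that the DLT-only restriction applies to PLX3397 alone. State there and in Section 16.1 that during radiotherapy temozolomide is interrupted or discontinued according to label Table 1, with its alopecia, nausea and vomiting exception, whether or not a DLT has occurred. Reproduce that table in Section 16.1, and keep Tables 7 and 8 for the adjuvant period.

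A useful clarification, on which the conclusion does not depend, is how missed temozolomide days count toward DLT evaluability. The replacement rule in Section 13.13.1 counts only missed PLX3397 days.

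The cost is amendment wording in two sections. No new procedure is needed, because weekly counts are already scheduled. The drawback is slightly more variable temozolomide exposure between patients in the DLT window.
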